13.4 Appendix 4. Sample Post-Call Survey

Blank, Grant, OxIS 2019 Questionnaire. All Parts (January 30, 2019). Available at SSRN: https://ssrn.com/abstract=3522118

Brooke J. Systems Usability Scale. In: Jordan P, Thomas B, Weerdmeester W, editors. Usability Evaluation In Industry Taylor & Francis; 1996. p. 189–194.

Parmanto B, Lewis AN Jr, Graham KM, Bertolet MH. Development of the Telehealth Usability Questionnaire (TUQ). Int J Telerehabil 2016 Jul 1;8(1):3–10. PMID:27563386

Demographic Questions

- 1. AGE: In what year were you born?
 - a. (If refuse to answer): Would you mind indicating which of these age bands you are in: 18-24, 25-34, 35-44, 45-54, 55-64, 65-74, 75-84, 85+
- 2. GENDER*: How do you currently describe your gender identity?
 - a. *Note: in the OxIS, gender was assessed 'by observation'. The wording of this question is therefore taken from a different source (Hughes, Camden, & Yangchen, 2016)
- 3. FAMILY:
 - a. Are you...? Single, Married, Living together with a partner, Divorced/separated, Widowed
 - b. How many adults live in your household (people age 18 or more)? [WRITE IN]
 - c. How many children (people age 17 or less) live in your household? [WRITE IN]
- 4. ETHNICITY: To which of these groups do you consider you belong?
 - a. ASIAN: of Indian origin
 - b. ASIAN: of Pakistani origin
 - c. ASIAN: of Bangladeshi origin
 - d. ASIAN: of Chinese origin
 - e. ASIAN: of any other origin (WRITE IN) ______
 - f. BLACK: of African origin
 - g. BLACK: of Caribbean origin
 - h. BLACK: of other origin (WRITE IN) _____
 - i. WHITE: of British origin
 - j. WHITE: of Scottish origin
 - k. WHITE: of Welsh origin
 - I. WHITE: of any other origin (WRITE IN) ______
 - m. OTHER (WRITE IN)
 - n. Don't know
- 5. URBAN: Would you describe the place where you live as a big city, the suburbs or outskirts of a big city, a small city or town, a country village, or, a farm or home in the country?
 - a. A big city
 - b. The suburbs or outskirts of a big city
 - c. A small city or town
 - d. A country village
 - e. A farm or home in the country
 - f. Other
 - g. Don't know

- 6. INCOME: The incomes of households differ a lot in Britain today. Here is a table showing the range of incomes that people have. Which option best represents the total income of your household before tax? Please select one answer only.
 - a. Up to £12.500 per year
 - b. £12.500 up to £20.000 per year
 - c. £20.000 up to £30.000 per year
 - d. £30.000 up to £40.000 per year
 - e. £40.000 up to £50.000 per year
 - f. £50.000 up to £60.000 per year
 - g. £60.000 up to £70.000 per year
 - h. £70.000 up to £80.000 per year
 - i. Over £80.000 per year
 - j. Prefer not to say
- 7. EDUCATION: What is the highest educational or vocational qualification that you have or that you will receive if you complete your next set of exams?
 - a. No qualifications
 - b. 5 or more GCSE grades A-C
 - c. 4 or less GCSE grade A-C
 - d. GCSE grade D-G
 - e. 5 or more Scottish Standard Grades, grades 1-3
 - f. 4 or less Scottish Standard Grades, grades 1-3
 - g. 5 or more O Grades, grades 1-3 (Scottish Ordinary Grades)
 - h. 4 or less O Grades, grades 1-3 (Scottish Ordinary Grades)
 - i. Scottish Standard Grades, grades 4-7
 - j. Scottish Highers (either SCE or SQC)
 - k. Scottish Certificate Sixth Year Studies
 - I. SVQ level 1 or 2 (Scottish Vocational Qualifications)
 - m. SVQ level 3 (")
 - n. SVQ level 4 (")
 - o. SVQ level 5 (")
 - p. CSEs
 - q. 5 or more O levels
 - r. 4 or less O levels
 - s. GCE A levels or equivalent
 - t. NVQ level 1 or 2
 - u. NVQ level 3 or 4
 - v. NVQ level 5
 - w. GNVQ Foundation
 - x. GNVQ Intermediate
 - y. GNVQ Advanced
 - z. Certificate or Diploma of Higher Education
 - aa. HND (Higher National Diploma)
 - bb. Bachelor's degree
 - cc. Graduate Certificates and Diploma
 - dd. Post-degree professional qualification (eg banking accountancy, architecture, etc.)
 - ee. Master's Degree

- ff. Doctoral Degree
- gg. Don't know
- 8. EMPLOYMENT: Which of these descriptions best describes your current situation?
 - a. Working Full time (30 hours a week or more)
 - b. Working Part time (8-29 hours a week)
 - i. If (a) or (b): Apart from working, do you also study? (yes / no / DK)
 - c. Retired
 - d. Unemployed
 - e. Permanently sick or disabled
 - f. In community or military service
 - g. Undergraduate Student
 - h. Post graduate student
 - i. In full time education (not higher degree)
 - j. In part time education (not higher degree)
 - i. If (g)-(j): And apart from studying, do you also work? (yes / no / DK)
 - k. Doing housework, looking after children or other persons

System Usability Scale

Rated on a 5-point Likert scale, from 'Strongly Disagree' (1) to 'Strongly Agree' (5)

- 9. I think that I would like to use this system frequently.
- 10. I found the system unnecessarily complex.
- 11. I thought the system was easy to use.
- 12. I think that I would need the support of a technical person to be able to use this system.
- 13. I found the various functions in this system were well integrated.
- 14. I thought there was too much inconsistency in this system.
- 15. I would imagine that most people would learn to use this system very quickly.
- 16. I found the system very awkward to use.
- 17. I felt very confident using the system.
- 18. I needed to learn a lot of things before I could get going with this system.

Telehealth Usability Questionnaire

Rated on a 7-point Likert scale, from 'Disagree' (1) to 'Agree' (7). It has been adapted slightly to fit the particular context of this study.

- 19. Telehealth improves my access to healthcare services.
- 20. Telehealth saves me time traveling to a hospital or specialist clinic.
- 21. Telehealth provides for my healthcare needs.
- 22. It was simple to use this system.
- 23. It was easy to learn to use the system.
- 24. The way I interact with this system is pleasant.
- 25. I like using the system.
- 26. The system is simple and easy to understand.
- 27. This system is able to do everything I would want it to be able to do.
- 28. I could easily talk to DORA.
- 29. I could hear **DORA** clearly.
- 30. I felt I was able to express myself effectively.
- 31. I think the visits provided over the telehealth system are the same as in-person visits.

- 32. Whenever I made a mistake using the system, I could recover easily and quickly.
- 33. The system gave error messages that clearly told me how to fix problems.
- 34. I feel comfortable communicating with **DORA**.
- 35. Telehealth is an acceptable way to receive healthcare services.
- 36. I would use telehealth services again.
- 37. Overall, I am satisfied with this telehealth system.

13.5 Appendix 5. Topic Guide for Semi-Structured Interviews

The topic guide was developed based on the Theoretical Framework of Acceptability (TFA) [16], which was created to provide a framework for assessing the multiple facets of acceptability of health interventions. The TFA has seven components: "1) affective attitude, 2) burden, 3) ethicality, 4) intervention coherence, 5) opportunity costs, 6) perceived effectiveness, and 7) self-efficacy" [16].

Interview questions

* Before the call

- 1. What did you expect the experience of talking to **DORA** to be like before you received the call?
- 2. How did you feel about talking to DORA before you received the call?
- 3. What, if any, concerns did you have before you received the call?
- 4. How well did you understand the intervention before you received the call?
- 5. What benefits or losses did you think you would experience when you received the call?
- 6. How successful did you think **DORA** would be at delivering the follow-up before you had the call?
- 7. How confident were you that you would be able to interact with **DORA** before you received the call?
- * During the call
 - 1. How did you feel about your experience interacting with **DORA**?
 - 2. How much effort did interacting with DORA take?
 - 3. What concerns, if any, did you have while talking with DORA?
 - 4. How well did you understand how the call worked while you were talking to DORA?
 - 5. What benefits or losses did you experience while you were talking to DORA?
 - 6. How much confidence did you have in **DORA's** ability to perform the follow-up assessment while you were talking to **DORA**?
 - 7. How comfortable and confident were you in your ability to interact with **DORA** while you were on the phone?
- * After the call
 - 8. Looking back on the experience now, how do you feel about using **DORA** to perform follow-up appointments?
 - 9. Looking back on the experience now, how much effort did interacting with DORA take?
 - 10. Looking back on the experience now, what concerns, if any, do you have about DORA?
 - 11. Looking back on the experience now, how well do you understand how DORA worked?
 - 12. Looking back on the experience now, what do you think you gained or lost by having your follow-up assessment with **DORA**?
 - 13. Looking back on the experience now, how well do you think **DORA** performed at conducting your follow-up assessment?
 - 14. Looking back on the experience now, how confident would you be having another interaction with **DORA**?
- * General feedback
 - 15. What would you suggest to make the experience of using **DORA** better?
 - 16. How willing would you be to use DORA again?
 - 17. If you had the choice between no follow-up / a face-to-face appointment (depending on clinical site) and **DORA**, which would you choose and why?
 - 18. Is there anything else you'd like to mention?

13.6 Appendix 6. Imperial Historical Recruitment Audit Data

Purpose

To provide real world evidence for assumptions made in modelling of recruitment numbers and study planning.

Audit

We audited all bookings in the cataract one-stop-clinic for the month of October 2020. After discussion with the head of the cataract pathway, it was felt this was the most representative of what the cataract pathway will likely look like in May-July 2021 assuming there is COVID recovery of a similar trajectory to the first wave. It is anticipated there will be 3 consultant-led one-stop clinics running in July to address the backlog. Of note, the general pre-assessment pathways have not been audited.

Key findings

Clinic capacity and utilisation - All October one-stop data

- 33 patients were booked across 4 clinics
- 8.25 patients on average per clinic
- 88% (29/33) attended their one-stop appointments

Conversion rate

- Of all patients booked, 76% proceeded for surgery (25/33)
- Or, of those attending, 86% proceeded to surgery (25/29)

Demographics

- Mean age was 71.5
- This was the first eye for 52% of patients

Inclusion/Exclusion

- 100% (29/29) of those attending were listed for routine cataract surgery
- 10% (3/29) required a translator (Tamil, Punjabi, Arabic)
- 1 patient (3%) had dementia and would not have been able to consent
- Overall, of all attending patients, 76% (29/33) would have been eligible for trial inclusion.

Withdrawal

- No patients in this cohort had unexpected surgical complications
- 1 patient (4%) attended AnE before follow up with a corneal abrasion and would have been withdrawn from **DORA** per our current protocol.

Follow up

- 95% (24/25) of patients attended post-op follow up
- **21%** (7/25) of patients had a documented complication requiring management change at their post-op followup.
 - \circ 6 of these patients were uveitis
 - 4 of which were given maxidex and discharged
 - 1 was given maxidex with phone follow up

- 1 was given maxidex and listed for 2nd eye.
- 1 patient has post-op cystoid macular oedema and maxidex requiring medical retina review.

Pathway

- The mean time between one-stop appointment and surgery was **9.88 days.**
 - The range was from 2 days to 62 days
 - **16 patients** had their operations in under 1 week
- Mean time between surgery and first follow up was 24.33 days.
- A number of patients were followed up under the 21 day point

Comparison with initial estimates

| | Imperial | Imperial |
|--------------------------------------|-----------------------|-----------------------|
| | One-stop (Projected 3 | One-stop October 2020 |
| | clinics per week from | One-stop October 2020 |
| Current Numbers Assessed | | |
| Mean Patients assessed per clinic | 10 | 7.25 |
| Clinics per week | 3 | 1 |
| Mean Patients Assessed per week | 30 | 7.25 |
| Eligibility Assumptions | | |
| % proceeding to surgery | 80% | 86% |
| % routine cases | 80% | 100% |
| % eligible for trial | 80% | 76% |
| % dropout due to complicated surgery | 5% | 0% |
| Screening | | |
| Compound daily eligibility rate | 49% | 65% |
| Number of days screening | 2 | 1 |
| Patients screened per week | 10 | 5 |
| Estimated recruitment | | |
| % consenting to trial | 90% | 90% |
| Estimated recruited per week | 9 | 4 |
| Duration of trial (weeks) | 26 | 27 |
| Estimated recruitment over trial | 228 | 115 |

Conclusions

- Based on these samples our projections were conservative apart from % eligible for trial
- Based on these projects even 2 clinics per week should allow us to meet a recruitment number of over 200 at Imperial.
- Recruiting from pre-op assessment will be required to meet aim of >400 patients

13.7 Appendix 7. Oxford Historical Recruitment Audit Data

All bookings for cataract surgery pre-assessments at the Oxford University Hospitals NHS Foundation Trust for October were audited to provide evidence for an estimate of the recruitment sample size. Assuming there is a recovery from the Covid-19 pandemic of a similar trajectory to the first way, this was determined to be the most representative of what the cataract pathway will likely look like in May-July 2021. The audit report was produced on 21 January, 2021.

Purpose

To provide real world evidence for assumptions made in modelling of recruitment numbers and study planning.

Audit

We audited the cataract clinic pre-op assessment clinics in October 2020. The clinic numbers were reviewed for the entire month, and the first 50 consecutive patients were reviewed in detail. It was felt this was the most representative of what the cataract pathway will likely look like in May-July 2021 assuming there is COVID recovery of a similar trajectory to the first wave.

Key findings

Clinic capacity and utilisation - all October data

- 160 patients were booked across 21 clinics
- 7.6 patients on average per day
- 96% (50/52) attended their one-stop appointments
- Only 1/160 was booked as a telephone assessment

Conversion rate (reviewing first 50 consecutive patients)

- Of all patients booked, 86% proceeded for surgery (45/52)
- Of all patients that attended, 90% were listed for surgery directly (45/50)
 - 2 were asymptomatic and discharged, 3 were referred to clinic and subsequently listed
 - Including those listed from clinic- 48/50, 96% were listed for surgery.

Demographics

- Mean age was 76.36
- 17 male: 33 female
- This was the first eye for 78% of patients

Inclusion/Exclusion

- 96% (46/48) of those attending were listed for routine cataract surgery
- 2% (1/48) required a translator
- 2 patients (4%) had learning difficulties and would not have been able to consent (the patient with learning difficulties also had surgical complexities)
- Overall, of all attending patients, 92% (44/48) would have been eligible for trial inclusion.

Pathway

- To date 30/44 (68%) of the patients listed have had cataract surgery
- The mean time between one-stop appointment and surgery was 30 days.
 - The range was from 0 days to 79 days
 - 3 patients had their operations in under 1 week

Withdrawal

- 6.6% (2/30) patients in this cohort had unexpected surgical complications 1 iris prolapse and 1 needing sutures
- The 2 patients with complications attended a planned clinic appointment and were discharged.
- 1 patient attended ED with CMO 10 weeks post procedure, 1 called eye casualty with red eye 6 weeks post procedure but did not need review

Follow up

• Only the 2 patients with unexpected complications had planned clinic appointments

| | Oxford | Oxford | Oxford |
|---|--------------------------------|---------------------------------------|--|
| | Pre-assessment October 2020 | Pre-assessment (Study projections) | Phone pre-assessment (2nd eye) (Study projections) |
| Current Numbers Assessed | | | |
| Mean Patients assessed per clinic | 7.6 | 12 | 4 |
| Clinics per week | 5 | 5 | 5 |
| Mean Patients Assessed per week | 39.5 | 60 | 20 |
| Eligibility Assumptions | | | |
| % proceeding to surgery | 90% | 90% | 90% |
| % routine cases | 96% | 80% | 80% |
| % eligible for trial | 92% | 90% | 90% |
| % dropout due to complicated surgery | 6.6% | 5% | 5% |
| Screening | | - | |
| Compound daily eligibility rate | 74% | 62% | 62% |
| Number of days screening | 2 | 2 | 2 |
| Patients screened per week | 11 | 15 | 5 |

Comparison with initial estimates

| Estimated recruitment | | | |
|----------------------------------|-----|-----|-----|
| % consenting to trial | 90% | 90% | 90% |
| Estimated recruited per week | 10 | 13 | 4 |
| Duration of trial (weeks) | 26 | 26 | 26 |
| Estimated recruitment over trial | 264 | 346 | 115 |

Conclusions

- The spread between F2F and telephone clinics was different to previously predicted, with only 1 patient in October having a telephone appt booked.
- Similar rates of patients that are potentially eligible in October 2020 compared to previous estimates
- Based on these projections even 2 clinics per week should allow us to meet a recruitment number of over 200 at Oxford

A Clinical Investigation of an Autonomous Phone Conversational Agent for Cataract Surgery Follow-up

NCT05213390

30 August 2022

Statistical analysis plan

Using the variables:

- doraoutcomeupdate (0 = pass, no review, 1 = fail, needs review)
- supervisoroutcomeupdate (0 = pass, no review, 1 = fail, needs review)

Primary outcome: Agreement between Dora and clinician for overall outcome decision and each symptom (x5)

- Inter-rater reliability (kappa)
- Accuracy (%)
- Data regarding true/false negatives/positives

	Clinician: follow-up (1)	Clinician: no follow-up (0)
Dora: follow-up (1)	ТР	FP
Dora: no follow-up (0)	FN	TN

• Sensitivity, specificity, AUC

Secondary outcomes

Clinical safety: Comparison with real complication rate

*Note: please do this analysis three times, once for each of the three complication measures
Data regarding true/false negatives/positives (Tables 2-3)

	Complications: 3 month audit	No complications: 3 month audit
Dora: follow-up	ТР	FP
Dora: no follow-up	FN	TN

- Sensitivity, specificity, AUC
- Variables
 - Dora follow up: "doraoutcomeupdate"
 - Complications:
 - "hospital-review-within-3-months"
 - 0 = no hospital review, 1 = hospital review
 - "unexpected-change-management"
 - 0 = no unexpected change management, 1 = unexpected change management

EUR ING [name] MA MSc MBA MPA PhD CEng FBCS Associate Professor of eHealth

"unplanned-hospital-rev"

• 0 = no hospital review, 1 = hospital review

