8.2.5 Outcomes

8.2.5.1 Primary Outcomes

Agreement

The primary outcome of the study is to establish preliminary safety evidence by evaluating the level of agreement between **DORA** and the expert human clinician on symptom and overall management plan decisions.

To evaluate agreement, **DORA's** ability to classify five key symptoms from the conversation will be compared with a supervising clinician's classification of the same five symptoms: redness, pain, reduced vision, flashing lights, and floaters (see Table 5). For this study, the supervising clinician's decision - made based on the information from the call with **DORA's** decision masked - is considered the gold-standard for evaluation. Both **DORA** and the supervising clinician (masked to each other) will independently indicate for each symptom, whether the symptom is:

- 1. Absent (e.g. no pain)
- 2. Present but not clinically significant (e.g. mild gritty sensation)
- 3. Present and clinically significant (e.g. deep and persistent pain)
- 4. Insufficient information for classification

The agreement between **DORA** and the clinician on the patient's management plan will be evaluated in the same way as the symptoms. **DORA** and the clinician will independently select one of the following options for the patient's management plan:

- 1. Passes check (patient continues to next step of their care as planned, e.g., Discharge from hospital care, add to waiting list for second eye surgery, or continue routine follow-up in clinic for another ophthalmic condition)
- 2. Needs clinical assessment relating to the cataract surgery

Ability to gather sufficient information

To evaluate **DORA's** ability to gather enough information for a clinician to decide a patient's management plan and the necessity for the clinician to ask clarifying questions will be assessed. If clarifying points are necessary for the clinician to make a decision, the clinician will ask the necessary questions, and then document updated assessments for symptoms and overall management (see Figure 5). Either 12 or 18 data points will be collected from each call depending on if clarifying questions are asked.

• Every Conversation

- o 5 symptom decisions from DORA + 1 clinical decision from DORA
- o 5 symptom decisions from Clinician + 1 management plan from Clinician
- If clarifying questions asked
 - Post-clarification 5 symptom decisions from Clinician + 1 management plan from Clinician

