This will allow us to test the hypothesis that clarifying questions affect the clinical management plans (see Table 5).

| Primary Outcome | Outcome Measure |
|-----------------|---|
| Agreement | Whether or not the clinician had to interrupt the call to ask clarifying questions Inter-rater reliability: the degree of agreement between DORA and the clinician on their assessments of the individual symptoms and the management plan |

Table 5. Primary Outcome Measurement

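### Does the SAP leave the clinician decision in the primary kappa undefined, and drop the interruption measure from the primary outcome?

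*SAP*

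**What the plan says.** The SAP opens with two fields for the overall decision, "doraoutcomeupdate (0 = pass, no review, 1 = fail, needs review" and "supervisoroutcomeupdate (0 = pass, no review, 1 = fail, needs review". From these come kappa, accuracy, the two-by-two table, sensitivity, specificity and AUC. The SAP gives the codes but not the point in the call at which each decision was taken. Its secondary section covers clinical safety only and uses DORA's field alone.

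Protocol section 8.2.5.1 defines the data. Every call yields "5 symptom decisions from DORA + 1 clinical decision from DORA" and a matching clinician set. If the clinician has to clarify, the clinician will "then document updated assessments for symptoms and overall management", which adds a third set: "Post-clarification 5 symptom decisions from Clinician + 1 management plan from Clinician". The reference standard is the clinician's decision "made based on the information from the call with" DORA's own decision hidden.

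Table 5 in the same section lists two measures under the primary outcome: inter-rater reliability, and "Whether or not the clinician had to interrupt the call to ask clarifying questions". The text just above the table says the data will serve to "test the hypothesis that clarifying questions affect the clinical management plans". Section 8.5.1 names kappa as the primary analysis and does not mention interruptions.

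**The concern.** The protocol uses the idea of an update only for the clinician's assessment after clarification, and the SAP's clinician field has update in its name. A reader could conclude that the primary kappa compares DORA with a clinician who has since obtained answers DORA did not elicit. That would no longer measure agreement on the same conversation, and two analysts could get different primary results from one dataset.

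The missing interruption analysis seems to compound this. A call in which the clinician had to step in can still count as agreement, and the SAP's own output would not show how often that happened. Since the research question is whether DORA can identify who needs follow-up, agreement without the interruption rate would flatter a system that often needed help.

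**Working it through.** **Which clinician decision is meant.** Four places in the protocol bear on it.

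1. Section 8.2.3, Stage 3: DORA and the clinician each record a management decision independently. Clarifying questions come in Stage 3a, which is optional and follows.
2. Section 8.2.5.1, Agreement: both raters are masked to each other and classify the same conversation. The gold standard is the clinician's masked, call-based decision.
3. Section 8.2.5.1, data list: one DORA set and one clinician set belong to every conversation. The set after clarification is listed separately, and the updated assessments are described under the sub-heading on gathering sufficient information, not under Agreement.
4. The symptom scale includes a category for insufficient information, which mainly makes sense before clarification.

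Together these point to the Stage 3 decision. The field name does not contradict them: `doraoutcomeupdate` has the same suffix although the protocol gives DORA one decision per call, so the suffix cannot reliably mark a value after clarification.

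**Where interruptions are planned.** Section 8.2.5.2 (Feasibility) logs every interruption and clarifying question, asks for the reason, and captures the clinician's plan before and after clarification where information was insufficient. Table 6 names the proportion of calls completed without intervention, which largely mirrors the Table 5 measure. With 520 calls (the protocol's required sample size) the 95% half-width of such a proportion is 1.96 × √(p(1−p)/520): 2.6 points at an assumed 10%, 3.4 at 20%, 3.9 at 30%.

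**How far kappa could move if the later decision were used.** The documents give no referral rate, expected kappa or clarification rate, so all inputs except 520 are assumed. Take 20% referred by the clinician, DORA sensitivity 0.80, specificity 0.90.

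- Cells: TP 83.2, FP 41.6, FN 20.8, TN 374.4.
- Observed agreement: (83.2 + 374.4)/520 = 0.880.
- Chance agreement: (124.8 × 104 + 395.2 × 416)/520² = 0.656.
- Kappa: (0.880 − 0.656)/(1 − 0.656) = 0.651; asymptotic SE 0.040; 95% CI 0.572 to 0.730.

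Hold DORA's decision fixed and let clarification change the clinician's plan, spread in proportion over the affected cells:

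| Plans changed | All toward DORA | All away from DORA | Half each way |
|---|---|---|---|
| 5 (1%) | 0.681 | 0.627 | 0.654 |
| 13 (2.5%) | 0.727 | 0.588 | 0.657 |
| 26 (5%) | 0.802 | 0.528 | 0.663 |

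Only the one-directional 5% rows leave the interval, and the upper one needs 26/62.4 = 42% of discordant calls to flip.

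A lower referral rate is less forgiving. With 10% referred and sensitivity and specificity both 0.90, the cells are 46.8, 46.8, 5.2 and 421.2, and kappa is (0.900 − 0.756)/(1 − 0.756) = 0.59 (SE 0.050, 95% CI 0.49 to 0.69). If 2% of plans change and every change falls in one cell, kappa becomes:

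- 0.48 if TP become FP;
- 0.69 if FP become TP;
- 0.53 if TN become FN, with sensitivity falling from 0.90 to 0.75.

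At 5% the three values are 0.29, 0.82 and 0.46.

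**The case for a change.** The strongest case for a change is that the SAP should stand on its own. It is the later document, it names the fields the analyst will use, and it never ties them to Stage 3. Section 8.5.1 speaks only of the decision made. In the 10% referral scenario a one-sided change in 2% of plans already takes kappa to the edge of its sampling interval or just past it, so the choice could matter. Table 5 places the interruption measure under the primary outcome, and collecting data does not oblige anyone to report them. Section 8.2.3 also lets the clinician break in at any point, so in some calls even the Stage 3 decision may follow help.

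Part of this stands. The timing is not written in the SAP, the interruption measure is not carried over, and how to count a call interrupted before Stage 3 is left open. But the larger kappa shifts put every change in one cell on assumed rates, and they arise only if the analyst departs from the protocol's own reading. Calls with early help are still logged and count against the proportion free of intervention. The SAP also omits usability, the promoter score and costs. It is a short instruction for agreement and safety, so leaving interruptions out does not show that the measure was abandoned.

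**Conclusion.** No change follows. The gap is one that analysts fill sensibly: the protocol points to DORA's single decision against the clinician's masked Stage 3 decision, and it separately plans the interruption log, the intervention-free proportion and the comparison of plans before and after clarification. Nothing in the documents shows that a wrong field is used. The safety tables do not use the clinician's field, so the ambiguity does not reach them.

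The size cannot be derived from the documents. On the assumed 20% referral case kappa stays within 0.57 to 0.73 for any of the tabulated changes up to 2.5% of calls, and at 0.65 to 0.66 when changes balance. On the assumed 10% case, changes confined to one cell could move it further. This rests on the reading of sections 8.2.3 and 8.2.5.1 above; a data dictionary, which is not among the documents, would settle what the suffix means.
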